6.1 TRIAL FLOW CHART

6.2 Study Flow Chart

Trial Period:	Screening Phase		reatment Follow-Up Cycles ^a									Long-Term Follow-Up			
Treatment Cycle/Title:	Pre- screening (Visit 1)	Main Study Screening (Visit 2)	1	2	3	4	End of Treatment / Re-evaluation	Post-treatment			As needed for trial data interpretation				
Scheduling Window (Days):		-28 to -1 days	1	W (± 7	eek days) ^b	Month 3 $\pm 7 \text{ days}^{c}$		(± 1	nth) (± 2 months)		s) 36	throughout and after the study period as determined by the Principal Investigator		
Administrative Procedures			_				,	_							
Informed Consent	X		Г	l	l		Ι	Г			Ι				I
LOH evaluation	X														
Tobacco and alcohol use history	X						X	X	X	X	X	X	X	X	
Prior oral cancer history	X														
Inclusion/Exclusion Criteria		X													
Demographics and Medical History		X													
Concomitant Medication Review		X													
Trial Treatment Administration			X	X	X	X									
Oral Cancer-free Survival Status															X
Clinical Procedures/Assessi	nents														•
Review Adverse Events		X		X	X	X	Xa								1
Physical Examination		X		X	X	X	X ^a X	X	X	X	X	X	X	X	1
ECOG Performance Status		X													
Laboratory Procedures/Ass	sessments: an	alysis perfo	rmed	l by l	LOC	AL la	boratory				•				
Pregnancy Test – Urine or Serum �-HCG		Xª					Xª								
Urinalysis		X					X ^a								
CBC with Differential		X		X	X	X	X	Xa		X					
Comprehensive Serum Chemistry Panel		X		X	X	X	X	Xa		X					
T3, FT4 and TSH		X					X ^a	Xª							
Non-invasive Efficacy Meas	surements						_								
Oral lesion measurement		X					X			X					
Tumor Biopsies/Archival T				4 30										 	 

Trial Period:	Screening Phase		Treatment Cycles ^a				Follow-Up							Long-Term Follow-Up	
Treatment Cycle/Title:	Fitle: Prescreening (Visit 1)		1	2	3	4	End of Treatment / Re-evaluation	Pos			ost-tro	eatme	nt	As needed for trial data interpretation	
Scheduling Window (Days):		-28 to -1 days	1	W (± 7 d	eek days 7) ^b	Month 3 ± 7 days ^c	(± 1 month)		month) (± 2 months)				s) 36	throughout and after the study period as determined by the Principal Investigator
Archival or Newly Obtained Tissue Collection ^d	X														
Newly Obtained Tissue Collection		Xe					X			X					
Correlative Studies Blood Collection ^f	X			X			X			X				X	
Oral Swab Collection ^f	X			X			X			X				X	

^a To be performed only in subjects randomized to the experimental arm. Pregnancy test must be performed <72 hours prior to the first dose of study medication.

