7.1.2.1 Adverse Event (AE) Monitoring

7.1.2 Clinical Procedures/Assessments

The investigator or qualified designee will be responsible for assigning attribution of adverse events to the study drug. The investigator or qualified designee will assess each subject to evaluate for potential new or worsening AEs as specified in the Trial Flow Chart and more frequently if clinically indicated. Adverse experiences will be graded and recorded according to NCI CTCAE Version 4.0 (see Section 7.2)Toxicities will be characterized in terms regarding seriousness, causality, toxicity grading, and action taken with regard to trial treatment.

For subjects receiving treatment with pembrolizumab AEs of unknown etiology associated with pembrolizumab exposure should be evaluated to determine if it is possibly an event of clinical interest (ECI) of a potentially immunologic etiology (termed immune-related adverse events, or irAEs); see the separate ECI guidance document in the Appendix regarding the identification, evaluation and management of potential irAEs.

Please refer to section 7.2 for detailed information regarding the assessment and recording of AEs.

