For the purpose of this study, adverse events that in the opinion of the treating investigator are related to planned procedures (e.g., usual pain, usual bleeding, intra- or post-procedure electrolyte imbalances and other clinically insignificant laboratory abnormalities) will not be captured and/or reported.

Adverse events will only be recorded for patients that undergo randomization. Adverse events will be recorded from the time the patient is randomized through the end of treatment / reevaluation visit (month 3) or 90 days following cessation of treatment, whichever is longer.

Any new serious adverse event that occurs more than 30 days after last study drug administration should be reported if considered related to study drug (e.g., secondary cancer). Should a patient discontinue from or complete the study and commence subsequent anticancer therapy within 30 days of the last study drug administration, adverse events attributable to this subsequent therapy should not be recorded.

Laboratory abnormalities are usually not recorded as adverse events; however, signs and/or symptoms that are associated with laboratory findings requiring study withdrawal, dose modification, or medical intervention (e.g., anemia requiring transfusions or hyperglycemia requiring treatment) or other abnormal assessments (e.g., ECG, radiographs, vital signs) must be recorded as adverse events (or serious adverse events) if they meet the definition of an adverse event (or serious adverse event). In addition, laboratory abnormalities marked as clinically significant should also be recorded as adverse events. The investigator will report the most severe grade of the clinically significant laboratory abnormality and will evaluate its relationship to the study drug and clinical condition.

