7.3.1. Immediate Reporting Serious Adverse Events to Merck

A serious adverse event is any adverse event occurring at any dose or during any use of Merck's product that:

- Results in death;
- Is life threatening;
- Results in persistent or significant disability/incapacity;
- Results in or prolongs an existing inpatient hospitalization;
- Is a congenital anomaly/birth defect;
- Is a new cancer (that is not a condition of the study);
- Is associated with an overdose;
- Is another important medical event

Refer to Table 6 for additional details regarding each of the above criteria.

Any serious adverse event, or follow up to a serious adverse event, including death due to any cause other than progression of the cancer under study that occurs to any subject from the time the subject is randomized through 90 days following cessation of treatment, or the initiation of new anti-cancer therapy, whichever is earlier, whether or not related to Merck product, must be reported within 5 working days of knowledge of the event to the IND Office and within 2 working days to Merck Global Safety.

ECIs (both non-serious and serious adverse events) identified in this guidance document from the date of first dose through 90 days following cessation of treatment, or 30 days after the initiation of a new anticancer therapy, whichever is earlier, need to be reported within 24 hours to the IND Office and within 2 working days to Merck Global Safety(Attn: Worldwide Product Safety; [contact]), regardless of attribution to study treatment, consistent with standard SAE reporting guidelines.

Non-serious Events of Clinical Interest will be forwarded to Merck Global Safety and will be handled in the same manner as SAEs.

Additionally, any serious adverse event, considered by an investigator who is a qualified physician to be related to Merck product that is brought to the attention of the investigator at any time outside of the time period specified in the previous paragraph also must be reported immediately to the IND Office and to Merck.

All subjects with serious adverse events must be followed up for outcome.

Product: MK-3475

Protocol/Amendment No.:

Table 6 Evaluating Adverse Events

An investigator who is a qualified physician, will evaluate all adverse events as to:

V4.0 CTCAE Grading	Grade 1	Mild; asymptomatic or mid symptoms; clinical or diagnostic observations only; intervention not indicated.		

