Toxicity data will be summarized by frequency tables. For the efficacy endpoint, intend-to-treat analysis will be applied to the eligible patients. For the toxicity endpoint, per-treated analysis will be used to include any patient who received the treatment regardless of the eligibility nor the duration or dose of the treatment received.

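### Adverse events are to be recorded in all randomized patients, but controls have no scheduled review after randomization and no place in the toxicity tables

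*Combined protocol and SAP*

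**What the plan says.** Section 7.2.1 fixes who is covered and for how long: "Adverse events will only be recorded for patients that undergo randomization", and "Adverse events will be recorded from the time the patient is randomized through the end of treatment" visit at month 3, or until 90 days after treatment stops if that is later. Neither sentence names an arm. Section 7.3.1 is equally broad for serious adverse events: it covers any such event "that occurs to any subject from the time the subject is randomized through 90 days following cessation of treatment", whatever its relation to the product.

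Section 7.1.2.1 leaves the timing of assessment to the flow chart: staff will "assess each subject to evaluate for potential new or worsening AEs as specified in the Trial Flow Chart and more frequently if clinically indicated". In the flow chart (section 6.2) the row "Review Adverse Events" is marked at main screening, at cycles 2, 3 and 4, and at month 3. The heading over the treatment cycles and the month 3 cell both carry footnote a: "To be performed only in subjects randomized to the experimental arm".

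Section 8.3 plans frequency tables for toxicity and defines the analysis set: "For the toxicity endpoint, per-treated analysis will be used to include any patient who received the treatment". The observation arm receives no treatment. The safety hypothesis in section 3.3 uses patients with advanced cancers as its benchmark.

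**The concern.** The recording rule and the schedule do not match. Staff reading 7.2.1 would record adverse events in controls, while staff working from the flow chart would never be prompted to ask about them. Whatever is recorded in controls then has no specified use in the analysis.

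This matters because the trial is open-label (5.2.3) and attribution rests on the investigator's judgement. Section 7.2.3 adds a default: a possible immune-related event of clinical interest is taken to be immune-related if no other cause is found. Background illness is plausible in this population. Section 8.2 plans 56 of the 104 patients with prior oral cancer, and smoking is common enough to be an allocation factor. A rate in untreated patients, asked in the same way, would help a reader judge how much of the treated-arm table is background.

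**Working it through.** **The sections side by side**

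| Section | Patients covered | After randomization |
|---|---|---|
| 7.2.1, adverse events | All randomized | Recorded to month 3, or to 90 days after treatment stops if later |
| 7.3.1, serious events | Any subject from randomization | Reported whether or not related |
| 6.2, adverse event review | Pembrolizumab arm only (footnote a) | Cycles 2, 3, 4 and month 3 |
| 8.3, toxicity set | Patients who received treatment | Frequency tables |

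The one unmarked review is at main screening, before the 7.2.1 window opens. Of the two end points in 7.2.1, only month 3 can apply to a control, who has no treatment to stop. Controls therefore have a recording window with no scheduled review inside it.

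The windows also differ in length. Four doses three weeks apart, without delays, put the last dose 3 × 21 = 63 days after the first. Adding 90 days gives 63 + 90 = 153 days, about 5 months, against 3 months for controls. Any two-arm table needs a common cut-off.

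The flow chart is damaged in the text available here: a stray footnote mark appears in the physical examination row. The reading above does not depend on it, because both the adverse event cell at month 3 and the cycle heading carry the mark.

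**What a two-arm table could show**

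The plan gives no figure to reproduce on this point. Inputs:
- 104 patients randomized 1:1, so 52 per arm (8.2).
- Treated rates p1 from the external lung cancer data in 4.2.4: 9.5% for grade 3-5 events, and 80/550 = 14.5% for immune-mediated events of any grade.
- Control rate p0: not in the documents; assumed at 0%, 2% and 5%.

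Half-width = 1.96 × √[p1(1 − p1)/52 + p0(1 − p0)/52].

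For p1 = 0.095 and p0 = 0.05: 1.96 × √(0.001653 + 0.000913) = 0.099.

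Power at two-sided 5% = Φ[(p1 − p0 − 1.96 × SE0)/SE1], where SE0 uses the pooled rate and SE1 the separate rates.

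| p1 | p0 | Difference (points) | 95% half-width | Power |
|---|---|---|---|---|
| 9.5% | 0% | 9.5 | 8.0 | 63% |
| 9.5% | 2% | 7.5 | 8.8 | 37% |
| 9.5% | 5% | 4.5 | 9.9 | 14% |
| 14.5% | 0% | 14.5 | 9.6 | 82% |
| 14.5% | 2% | 12.5 | 10.3 | 64% |
| 14.5% | 5% | 9.5 | 11.3 | 37% |

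These normal approximations are rough: 5% of 52 is only 2.6 expected control events, and with p0 = 0 the control arm adds no variance.

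Without controls only the treated-arm rate remains. Exact (Clopper-Pearson) intervals are 5/52 = 9.6% (3.2% to 21.0%) and 8/52 = 15.4% (6.9% to 28.1%).

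**The case against.** The strongest defence is that nothing planned goes missing. A reader might infer that the trial forfeits a randomized safety comparison that it meant to make. The documents do not support that: section 3.3 asks about the safety of pembrolizumab against an external benchmark, and the treated-patient set in 8.3 fits that question. It is a defensible choice for a phase 2 trial with an untreated control. This stands.

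A reader might also infer that control events surface solely when patients raise them. That is too strong. Serious events must be reported in any randomized subject. Assessment when clinically indicated is allowed. The month 3 blood count and chemistry panel carry no arm restriction, and 7.2.1 requires clinically significant laboratory abnormalities to be recorded. The gap is in scheduled review of non-serious symptoms.

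Nor do biopsy effects support the concern, since 7.2.1 already keeps usual procedure-related events out of the record.

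It can be said that a recording rule and a review schedule may coexist, and that the first sentence in 7.2.1 mainly serves to exclude non-randomized subjects. That softens the conflict but does not remove it: staff still cannot tell whether to ask controls about adverse events.

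Finally, adding a month 3 review for controls leaves one review against four in the treated arm. Tabulating everything side by side would favour controls. This objection is sound and limits what the fix may compare.

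**Conclusion.** The point holds as a minor one. Sections 7.2.1 and 7.3.1 cover all randomized patients, the flow chart and 7.1.2.1 schedule review after randomization in one arm only, and 8.3 analyses that arm only. Control events are collected unsystematically and not used, which leaves the safety objective without a concurrent background rate.

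The value of that rate is descriptive. A 95% half-width of roughly 8 to 11 points is as large as most of the differences considered, and power for grade 3-5 events is 14% to 63%. These figures rest on assumed control rates of 0% to 5% and on lung cancer rates carried over to patients with oral IEN. The conflict between the sections rests on none of them.

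**What to change.** - **Flow chart (6.2):** remove footnote a from the month 3 adverse event review, so that both arms are asked the same questions with the same recall period.
- **Sections 7.1.2.1 and 7.2.1:** bring the wording into line with the chart, and state that the recording window for controls closes at month 3.
- **Section 8.3:** keep the treated-patient table as the main safety summary. Add a descriptive table of both arms, by treatment actually received, over the common window from randomization to month 3.
- **Limits on comparison:** confine side-by-side reading to serious adverse events, month 3 laboratory findings and events elicited at the month 3 review. State that treated patients were also reviewed at cycles 2 to 4, so non-serious events first recorded at those visits are not comparable.

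The cost is a few minutes at a visit that controls already attend, modest data entry for about 52 patients, and one further table. The comparison will be imprecise and should be labelled descriptive.

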3.3 Secondary Objective(s) & Hypothesis(es)

(2) **Objective**: To determine safety and tolerability of pembrolizumab for patients with oral IEN

Hypothesis: Pembrolizumab will have similar or better toxicity profile as in patients with advanced cancers

(3) **Objective**: To determine the histologic and clinical response rates (in the subgroup of patients with clinically evident, measurable oral IEN lesions) to pembrolizumab

Hypothesis: Pembrolizumab will reverse histologic changes associated with oral IEN, and will reduce the size of clinically evident oral IEN lesions (i.e., leukoplakia and/or erythroplakia)

(4) **Objective**: To characterize the immune infiltrate in oral IEN lesions before and after treatment with pembrolizumab.

Hypothesis: Pembrolizumab will stimulate a specific, monoclonal / oligoclonal adaptive immune response

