Immune-Mediated AE Summary in patients with metastatic non-small cell lung cancer treated with pembrolizumab in the KEYNOTE-001 study

Category	Total N-550
Any, n (%)	80 (14.5)
Grade ≥3, n (%)	21 (3.8)
Led to death a, n (%)	1 (0.2)
Led to discontinuation, n (%)	15 (2.7)
Events resolved b, c, %	69.3

^aPneumonitis. ^bincludes all events of any grade, excluding hypothyroidism. ^cResolution is defined as a return to grade 0 or baseline. Data cutoff date: January 23, 2015

Adverse Events in Patients with Non-small Cell Lung Cancer Treated with Pembrolizumab in KEYNOTE-001*

Adverse Events	Any Grade	Grade 3-5
	no. of pati N=495 total	
Fatigue	96 (19.4)	4 (0.8)
Pruritus	53 (10.7)	0
Decreased appetite	52 (10.5)	5 (1.0)
Rash	48 (9.7)	1 (0.2)
Arthralgia	45 (9.1)	2 (0.4)
Diarrhea	40 (8.1)	3 (0.6)
Nausea	37 (7.5)	4 (0.8)
Hypothyroidism	34 (6.9)	1 (0.2)
Asthenia	24 (4.8)	5 (1.0)
Anemia	21 (4.2)	0
Dyspnea	21 (4.2)	19 (3.8)
Pyrexia	21 (4.2)	3 (0.6)
Decreased weight	19 (3.8)	2 (0.4)
Dry skin	18 (3.6)	0
Pneumonitis†	18 (3.6)	9 (1.8)
Elevation in aspartate aminotransferase	15 (3.0)	3 (0.6)
Vomiting	14 (2.8)	3 (0.6)
Dermatitis acneiform	13 (2.6)	0
Myalgia	13 (2.6)	0
Cough	12 (2.4)	0
Elevation in alanine aminotransferase	11 (2.2)	2 (0.4)
Chills	10 (2.0)	0
Constipation	10 (2.0)	2 (0.4)
Infusion-related reaction	15 (3.0)	1 (0.2)

^{*} Listed are events that were considered to be related to treatment by the investigator and were reported in at least 2% of patients.

[†] Included among patients with pneumonitis is one patient with grade 5 interstitial lung disease.

NCT02882282

(d) Selection of a short treatment course. The three-month treatment period utilized within this protocol is likely to reduce the incidence of adverse events and/or limit their duration.

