5.2.1.2 Dose Modification

Adverse events (both non-serious and serious) associated with pembrolizumab exposure may represent an immunologic etiology. These adverse events may occur shortly after the first dose or several months after the last dose of treatment. Pembrolizumab must be withheld for drug-related toxicities and severe or life-threatening AEs as per Table 3 below. See Section 5.6.1 and Events of Clinical Interest Guidance Document for supportive care guidelines, including use of corticosteroids.

Table 3

Dose Modification Guidelines for Drug-Related Adverse Events

Toxicity	Hold Treatment For Grade	Timing for Restarting Treatment	Discontinue Subject
Diarrhea/Colitis	2-3	Toxicity resolves to Grade 0-1.	Toxicity does not resolve within 12 weeks of last dose or inability to reduce corticosteroid to 10 mg or less of prednisone or equivalent per day within 12 weeks.
	4	Permanently discontinue	Permanently discontinue
AST, ALT, or	2	Toxicity resolves to Grade 0-1	Toxicity does not resolve within 12 weeks of last dose.
Increased Bilirubin	3-4	Permanently discontinue (see exception below) ¹	Permanently discontinue
Type 1 diabetes mellitus (if new onset) or	T1DM or 3-4	Hold pembrolizumab for new onset Type 1 diabetes mellitus or Grade 3-4 hyperglycemia associated with evidence of	Resume pembrolizumab when patients are clinically and metabolically stable.

NCT02882282

Toxicity	Hold Treatment For Grade	Timing for Restarting Treatment	Discontinue Subject							
Hyperglycemia		beta cell failure.								
Hypophysitis	2-3	Toxicity resolves to Grade 0-1	Toxicity does not resolve within 12 weeks of last dose or inability to reduce corticosteroid to 10 mg or less of prednisone or equivalent per day within 12 weeks.							
	4	Permanently discontinue	Permanently discontinue							
Hyperthyroidism	3	Toxicity resolves to Grade 0-1	Toxicity does not resolve within 12 weeks of last dose or inability to reduce corticosteroid to 10 mg or less of prednisone or equivalent per day within 12 weeks.							
	4	Permanently discontinue	Permanently discontinue							
Hypothyroidism	2-4	Therapy with pembrolizumab can be continued while treatment for the thyroid disorder is instituted	Therapy with pembrolizumab can be continued while treatment for the thyroid disorder is instituted.							
Infusion Reaction	3-4	Permanently discontinue	Permanently discontinue							

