Pneumonitis	umonitis 2 Toxicity resolves to Grade 0-1		Toxicity does not resolve within 12 weeks of last dose or inability to reduce corticosteroid to 10 mg or less of prednisone or equivalent per day within 12 weeks.							
	3-4	Permanently discontinue	Permanently discontinue							
Renal Failure or Nephritis	Renal Failure or 2 Toxicity resolves to Grade 0-1		Toxicity does not resolve within 12 weeks of last dose or inability to reduce corticosteroid to 10 mg or less of prednisone or equivaler per day within 12 weeks.							
-	3-4	Permanently discontinue	Permanently discontinue							
All Other Drug- Related Toxicity ²	3 or Severe	Toxicity resolves to Grade 0-1	Toxicity does not resolve within 12 weeks of last dose or inability to reduce corticosteroid to 10 mg or less of prednisone or equivalent per day within 12 weeks.							
•	4	Permanently discontinue	Permanently discontinue							

Note: Permanently discontinue for any severe or Grade 3 drug-related AE that recurs or any life-threatening event.

Dosing interruptions are permitted in the case of medical / surgical events or logistical reasons not related to study therapy (e.g., elective surgery, unrelated medical events, patient vacation, and/or holidays). Subjects should be placed back on study therapy within 6 weeks of the scheduled interruption, unless otherwise discussed with the Principal Investigator. The reason for interruption should be documented in the patient's chart. There will be no dose reduction permitted in this study.

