5.8.1 Discontinuation of Study Therapy

Subjects must discontinue therapy for the following reasons:

- Withdrawal / discontinuation from study.
- Worsening oral lesions requiring discontinuation from study therapy, in the opinion of the treating physician
- Unacceptable adverse experiences as described in Section 5.2.1.2
- Intercurrent illness that prevents further administration of treatment
- Investigator's or patient's decision
- The subject has a confirmed positive serum pregnancy test
- Development of oral cancer
- The subject is lost to follow-up

For patients that develop oral cancer during the study or for patients that are lost to follow up, only the procedures described under "Lon-Term Follow-Up" in section 6.0 will be performed.

If possible, subjects that discontinue therapy before completing 4 cycles of treatment should remain on study and continue to undergo study procedures and follow-ups as described in Section 6.0.

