^b If there are treatment delays, timing of subsequent cycles will be adjusted so that pembrolizumab is given every 3 weeks (± 7 days)

^c In subjects who had a treatment delay, evaluation should be postponed until at least 2 weeks after last dose of treatment

^d At any time point after enrollment, any archival or newly obtained tissue as part of standard of care for monitoring of oral IEN or newly developed oral cancer may be collected for correlative studies. This applies to any subject participating in the study from the time of enrollment, regardless of LOH or randomization status.

^e During the screening phase, newly obtained tissue collection may be performed within 12 months before randomization

^f For patients diagnosed with oral cancer during the study, extra blood collection and oral swabs collection may be performed approximately at the time of diagnosis of invasive cancer.

NCT02882282

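### Adverse event recording on pembrolizumab closes 90 days after the last dose, so late-onset non-serious immune events found at visits already scheduled would not reach the toxicity tables

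*Combined protocol and SAP*

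**What the plan says.** Section 7.2.1 records adverse events only for randomized patients, from randomization "through the end of treatment / reevaluation visit (month 3) or 90 days following cessation of treatment, whichever is longer". After that period, sections 7.2.1 and 7.3.1 ask only for serious events judged related to the drug. Section 7.3.1 stops reporting of non-serious Events of Clinical Interest at the same 90 days, or 30 days after new anticancer therapy if that is earlier.

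On timing, section 5.2.1.2 says of events that may be immunologic: "These adverse events may occur shortly after the first dose or several months after the last dose of treatment".

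The flow chart (section 6.2) marks adverse event review at screening, during the treatment cycles and at month 3, and not afterwards. Physical examination continues at every post-treatment visit. CBC and the "Comprehensive Serum Chemistry Panel" are marked in the first post-treatment column for the experimental arm only, and in the third post-treatment column for both arms. Thyroid tests are marked in the first post-treatment column, experimental arm only. Section 7.1.3 treats hematology and chemistry as safety evaluations.

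Safety is the first secondary objective in section 3.3: "To determine safety and tolerability of pembrolizumab for patients with oral IEN". Section 8.3 summarizes toxicity in frequency tables for patients who received treatment.

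**The concern.** The plan keeps examining patients and drawing safety labs after it has stopped recording non-serious adverse events. If a non-serious hepatic or skin event first appears at a later examination or lab draw, no rule in the protocol places it in the trial database. Section 5.2.1.2 itself warns of such late onset.

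These events bear directly on the question of tolerability. Section 4.2.1 accepts mild to moderate toxicity as reasonable in a high-risk population, and section 4.2.4 argues from a short course and from a 69.3% resolution rate in another population. Section 3.3 hypothesizes a toxicity profile similar to or better than that seen in advanced cancer. Leaving out late non-serious events moves the tables toward that hypothesis. Later reconstruction would be laborious, because section 7.1.1.7 keeps concomitant medications in the medical record and out of the trial database.

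**Working it through.** **Inputs.** Four doses, one every 3 weeks (Table 2, section 5.2). Closing rule: the later of month 3 and 90 days after cessation (section 7.2.1). Interruptions unrelated to therapy (section 5.2.1.2): "Subjects should be placed back on study therapy within 6 weeks of the scheduled interruption". Table 3 allows up to 12 weeks from the last dose for a toxicity to resolve. There are 104 patients randomized 1:1 (section 8.2), so 52 per arm. One month is taken as 30.44 days, and the first dose is assumed to fall on the day of randomization (day 1); a later first dose moves every closing date by the same lag.

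**The plan's own figure.** Section 4.2.4 says: "The three-month treatment period utilized within this protocol is likely to reduce the incidence of adverse events". Four 21-day cycles give 4 × 21 = 84 days, and 84 / 30.44 = 2.8 months. This agrees.

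**Closing date.** Doses fall on days 1, 22, 43 and 64. Closing day = last dose day + 90, with month 3 as the minimum. Elapsed months = (closing day − 1) / 30.44.

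- One dose: 1 + 90 = day 91, just short of month 3, so month 3.0 applies.
- Two doses: 22 + 90 = day 112; 111 / 30.44 = month 3.6.
- Three doses: 43 + 90 = day 133; 132 / 30.44 = month 4.3.
- Four doses on time: 64 + 90 = day 154; 153 / 30.44 = month 5.0 (4.8 to 5.3 if the last dose moves by 7 days).
- Four doses, one 6-week delay: 64 + 42 + 90 = day 196; 195 / 30.44 = month 6.4.
- Four doses, one 12-week gap in place of 3 weeks: 64 + 63 + 90 = day 217; 216 / 30.44 = month 7.1.
- Four doses on time, if cessation means the end of the last 21-day cycle: 64 + 21 + 90 = day 175; 174 / 30.44 = month 5.7.

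**Labs after closing.** The month headings of the flow chart are broken in the available text. The third post-treatment column also holds lesion measurement and tissue collection. Section 7.1.5 places biopsies at baseline and months 3 and 12, and section 10.4 records response at months 3 and 12, so this column is month 12. The gap is 12 − 5.0 = 7.0 months on time, 12 − 6.4 = 5.6 months with a 6-week delay, and 12 − 7.1 = 4.9 months with a 12-week gap. The header shows visit windows of 1 and 2 months; a visit 2 months early, at month 10, would still follow every closing date above.

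The month of the first post-treatment column is not legible. If the three columns after month 3 are evenly spaced up to month 12 (an assumption), it is month 6, which is 1.0 month after an on-time close. With a 6-week delay (month 6.4) it could fall inside the window, so it supports the point less firmly than month 12.

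**Other routes into the database.** Late serious related events are reportable without an end date (sections 7.2.1 and 7.3.1). The basic period for serious events reads 30 days after the last dose in one place and 90 days in the other, but that does not affect this point. Non-serious Events of Clinical Interest end at 90 days. Section 7.1.2.1 permits extra assessment when clinically indicated, and section 7.2.1 asks that clinically significant laboratory abnormalities be recorded as adverse events; neither extends the recording period.

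**Size, as an illustration.** The documents give no rate of late-onset non-serious immune events. For an assumed rate p among 52 treated patients, the expected number missed is 52p and the chance of at least one is 1 − (1 − p)^52:

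- p = 1%: 0.5 patients, 41%
- p = 2%: 1.0 patients, 65%
- p = 5%: 2.6 patients, 93%
- p = 10%: 5.2 patients, 99.6%

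**The case against.** The strongest reply is that the gap is one of degree. Ninety days already covers three months after the last dose, so section 7.2.1 does not contradict section 5.2.1.2. Late serious related events stay reportable, and section 7.2.1 lets a medically important event count as serious without hospitalization. All of this stands. What remains outside the rule is non-serious toxicity with onset after the 90 days.

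Three stronger readings are tempting, and the documents do not support them.

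- A reader might infer that unequal windows (about month 5 against month 3, since observation patients have no treatment to cease) bias a comparison of the arms. Section 8.3 tabulates toxicity only for treated patients and plans no between-arm test, so no planned result is biased.
- A reader might infer that persistent events are lost. An event that starts inside the window is recorded. Section 7.2.4 requires each change of grade within an episode to be recorded, Table 6 asks for start and stop dates, and serious events are followed to resolution or stabilization. At most, later updating of open non-serious events is not spelled out.
- A reader might infer that thyroid abnormalities would surface at the month-12 labs and be dropped. No thyroid test is marked there; the last is in the first post-treatment column.

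Nor is the share of the 36-month participation a fair measure of harm. That period was set for cancer follow-up and is not a toxicity risk period.

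**Conclusion.** The point holds for late-onset, non-serious, immune-related events in patients who received pembrolizumab. Followed as written, section 7.2.1 leaves them out of the tables that serve the first secondary objective, although examinations and safety labs that could reveal them are already scheduled. Late toxicity is therefore undercounted.

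The month-5 closing assumes four doses on time; early stoppers close sooner and delayed patients later, but all well before month 12. That month rests on matching the flow chart column with sections 7.1.5 and 10.4. The number of events missed cannot be derived from the documents; at assumed rates of 1% to 10% it is 0.5 to 5.2 of 52 patients, if all 52 allocated are treated. The primary analysis is untouched. This is a cheap improvement to the safety data, not an error that invalidates a planned result.

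**What to change.** In section 7.2.1, for patients who received pembrolizumab, record immune-related adverse events of any grade with onset up to the existing month-12 visit. Also record, at that visit, the status of events still open when the current window closes. In the flow chart, mark adverse event review at the existing post-treatment visits through month 12.

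The cost is some additional adverse event review and data entry at visits that already take place. No new visit, lab or procedure is needed. It is not free, because the review row has no mark after month 3.

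Applying the same window to the observation arm is optional and would give a background rate only. It would cost more there: as the flow chart reads, the post-baseline review marks apply to the experimental arm alone, so review would have to be added.
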